13.0 STATISTICAL CONSIDERATIONS

13.1 Study Design

This is a randomized double-blind placebo-controlled phase III trial of aspirin (300 mg daily) in non-metastatic HER2 negative breast cancer patients. Patients will be randomized 1:1 within stratum defined by: Hormone Receptor status (HR positive vs HR negative), body mass index (<30 vs ≥ 30 kg/m 2) and anatomic stage (Stage I/II vs III).

The primary objective of this trial is to compare the effect of aspirin versus placebo upon invasive disease free survival (iDFS).

13.2 Sample Size, Accrual Time and Study Duration

A stratified log-rank test will be used for the primary comparison of iDFS, with an overall one-sided Type I error of 0.025. Five year iDFS on placebo is assumed to be 77% based on results from the control arm of E5103. This study randomized 4994 patients to doxorubicin, cyclophosphamide, and paclitaxel plus or minus bevacizumab, and the patient population was similar to current eligibility criteria. An improvement in 5year iDFS to 82.2% would be considered clinically meaningful (HR = 0.75) and consistent with published data. Final analysis will occur at 381 iDFS events, in order to have 80% power to detect the target improvement.

A total sample size of 2936 patients will be enrolled in order to reach 381 iDFS events for final analysis. This assumes an accrual duration of 30 months including a 6 month ramp-up period to a maximum of 108 patients per month, and a constant hazard of loss-to-follow-up rate of 5% at 48 months in each arm.

An additional follow-up of 24 months is anticipated to reach final analysis, for a total study duration of 54 months from activation.

Because accrual was slower than anticipated, the eligibility criteria have been expanded although the sample size and overall analytic plan remain unchanged. Originally, subjects must have histologically confirmed invasive breast cancer and register within 12 months of initial diagnosis. The eligibility criteria have been extended to within 18 months of initial diagnosis for hormone receptor negative patients (HR-), and patients with hormone-receptor positive disease (HR+) would be eligible to participate within 10 years from initial diagnosis if there is no evidence of local/regional recurrence or metastatic disease. With the proposed change in study population, the primary objective will remain to compare the invasive disease free survival (iDFS) of patients randomized to receive aspirin (300 mg daily) versus placebo, and is defined as the interval from the defined as time from randomization to the first occurrence of any one of the following events for invasive disease: Distant recurrence, locoregional recurrence, ipsilateral or contralateral breast cancer, second primary (non-breast) invasive cancer or death from any cause as per section 13.3, and the primary analysis will be performed in an intention-to-treat manner, in which all patients including those who do not begin protocol therapy will be analyzed according to their assigned arm (13.3.3). The target effect-size will remain a 25% improvement in outcomes with the intervention (HR = 0.75), and under the assumption the risk of recurrence in HR+ disease is approximately constant even up to 20 years out from diagnosis (66), the number of iDFS events for final analysis would be reached under comparable timelines with the target sample size of 2936 patients. With the modification, the HR status stratification factor has been modified to be HR-positive patients that are less than or greater than 18 months out from initial diagnosis, and HR-negative patients, and a secondary analysis will be done to compare the efficacy in the subgroup of patients within 18 months of diagnosis, and explore outcomes and relationship to treatment in patients more than 18 months out from initial diagnosis with disease-free interval included as a covariate in multivariate regression models.

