13.4.2 Interim analysis for primary endpoint (iDFS)

Early stopping for futility is defined under a one-sided hypothesis of clinical benefit of aspirin and will be conducted using standard group sequential designs for phase III studies of time-to-event outcomes. Specifically, the Z-statistics from stratified log-rank tests will be calculated at each interim analysis. Futility boundaries will be defined using a Hang, Shih and DeCanis Gamma beta-spending function (parameter = -5) whereby the futility boundary at the first interim analysis is close to observing no treatment effect with aspirin (HR = 1) [23]. Interim monitoring for futility will begin at the first DSMB meeting to occur when 50% of expected events are observed and continue to coincide with the semi-annual calendar of the board.

In addition to the boundary and observed Z-statistics, the DSMB will be provided Kaplan-Meier product limit estimators to the survival functions for each arm, and the corresponding hazard ratio (corr. HR) and 95% CIs from a stratified Cox proportional hazard model for iDFS.

The following table provides boundaries under the assumed rates of accrual and target hazard rates of iDFS that results three interim analyses for futility starting at exactly 50% information.

	First Interim	Second Interim	Third Interim	Final Analysis
iDFS Events:N (%)	191 (50%)	247 (65%)	305 (80%)	381 (100%)
Months from activation	34	40	46	54
Futility Bound critical Z (corr. HR)	-0.192 (1.03)	0.385 (0.96)	0.988 (0.89)	-
Superiority Bound: critical Z (corr.HR)	-	-		1.96 (0.82)
Nominal Alpha (Superiority)	-	-		0.025
Accumulated Alpha	-	-		0.025
Accumulated Beta	0.015	0.033	0.071	0.194

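### In the section 13.4.2 monitoring table, the final accumulated beta of 0.194 is not attained by the printed design; with the printed bounds it is about 0.203 (minor table correction)

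*Combined protocol and SAP*

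**What the plan says.** Section 13.2 sets the primary comparison as a stratified log-rank test "with an overall one-sided Type I error of 0.025". On the control arm, "Five year iDFS on placebo is assumed to be 77"%. For the target, "An improvement in 5year iDFS to 82.2% would be considered clinically meaningful (HR = 0.75"). It concludes: "Final analysis will occur at 381 iDFS events, in order to have 80% power to detect the target improvement". Section 13.1 gives equal allocation: "Patients will be randomized 1:1 within stratum".

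Section 13.4.1 rules out early stopping for superiority, so all alpha is kept for the final analysis. Section 13.4.2 adds futility monitoring with a gamma beta-spending function (parameter -5). Its table projects the following:

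| | Look 1 | Look 2 | Look 3 | Final |
|---|---|---|---|---|
| iDFS events | 191 | 247 | 305 | 381 |
| Futility Z (corresponding HR) | -0.192 (1.03) | 0.385 (0.96) | 0.988 (0.89) | none |
| Superiority Z (corresponding HR) | none | none | none | 1.96 (0.82) |

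The last row of that table reads "Accumulated Beta 0.015 0.033 0.071 0.194".

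**The concern.** A final accumulated beta of 0.194 says that the monitored design has 80.6% power. That is more than the 80% in section 13.2, although the table adds three chances to stop for futility and does not relax the final bound to compensate. With the final bound fixed at 1.96, a futility look can turn a result that would have been significant into a stop. It can never do the reverse. Total beta with looks must therefore be at least the beta of the single test at 381 events. If that floor lies above 0.194, the table's rows do not describe one design.

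This table states the operating characteristics of the futility rule for the data and safety monitoring board (DSMB). The board should be able to read the true type II error from it. What is at stake is the accuracy of that statement. The type I error and the final decision rule are not affected.

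**Working it through.** **Inputs.** HR 0.75, one-sided alpha 0.025 and 381 events (13.2); 1:1 allocation (13.1); looks at 191, 247 and 305 events with futility Z -0.192, 0.385 and 0.988, final Z 1.96 (13.4.2). Loss to follow-up and follow-up time affect only when the 381st event arrives.

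**1. The plan's own figure.** The rates agree with the hazard ratio: ln 0.822 / ln 0.77 = 0.750. With the Schoenfeld formula, events = 4 × (1.960 + 0.8416)² / (ln 0.75)² = 4 × 7.849 / 0.08276 = 379.4, so 380. Freedman's formula gives 385. The stated 381 events for 80% power is reproduced.

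**2. Beta with no interim look.** Drift at 381 events = ln(4/3) × √381 / 2 = 0.28768 × 9.760 = 2.808. Beta = Φ(1.960 − 2.808) = Φ(−0.848) = 0.198, so power is 80.2%. This floor is already above 0.194.

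**3. Beta with the printed looks.** The Z statistics are jointly normal, with mean 2.808 × √(events/381) and correlation √(smaller events / larger events) between looks. Accumulated beta is one minus the probability of staying above every bound so far. Recursive integration and a multivariate-normal integral agree:

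| Events | 191 | 247 | 305 | 381 |
|---|---|---|---|---|
| Printed | 0.015 | 0.033 | 0.071 | 0.194 |
| From the printed bounds | 0.0146 | 0.0342 | 0.0711 | 0.2034 |

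Power is 79.7%. The looks cost 0.2034 − 0.1983 = 0.005. The first and third entries match, the second is slightly off (step 6), and the final entry does not match.

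**4. Other conventions.** None reaches 0.194:

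| Variant | Beta, no looks | Beta, with looks |
|---|---|---|
| Freedman drift | 0.204 | 0.209 |
| 216/165 event split from section 13.5 | 0.205 | 0.211 |
| HR from the rounded survival rates | 0.198 | 0.203 |
| Binding futility, final bound relaxed to 1.949 | not applicable | 0.2006 |
| Log-rank simulation, 6000 runs (SE 0.005) | 0.200 | 0.206 |

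The simulation is too coarse to separate 0.203 from its neighbours; the argument rests on the integration. Attaining 0.194 would take about 385 events with no looks. With the printed looks it would take about 390 events, or a final bound of about 1.923 (nominal alpha 0.027).

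**5. Where 0.194 probably comes from.** The gamma(-5) spending fraction is g(t) = (e^{5t} − 1)/(e^5 − 1). Multiplied by a total of 0.194:

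- t = 0.50: 0.0759 × 0.194 = 0.0147
- t = 0.65: 0.1682 × 0.194 = 0.0326
- t = 0.80: 0.3636 × 0.194 = 0.0705

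These round to the printed 0.015, 0.033 and 0.071. Solving for the bounds that spend these amounts at exactly 50, 65 and 80% information gives Z = -0.192, 0.358 and 0.988. The beta row thus follows a nominal budget of 0.194. That same design, with 1.96 at the end, also finishes at 0.203.

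**6. The second look.** The corresponding hazard ratio is exp(−2Z/√events). For Z 0.385 at 247 events, exp(−0.770/15.716) = 0.952, against the printed 0.96, and accumulated beta is 0.034 against the printed 0.033. For Z 0.358, exp(−0.716/15.716) = 0.955, which rounds to 0.96, and accumulated beta is 0.033. The printed HR and beta therefore fit 0.358, not 0.385. Final beta is 0.203 with either value.

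**The case against.** **Rounded inputs.** The strongest technical reply is that 0.75 is itself a rounded figure. At HR 0.7475, which rounds to 0.75, the printed bounds do give a final beta of 0.194. The same assumption then gives interim entries of 0.014, 0.032 and 0.067, against the printed 0.015, 0.033 and 0.071, so it does not explain the table. More generally, a first-look beta that rounds to 0.015 at a bound that rounds to -0.192 limits the drift to about 2.82. No-look beta is then at least about Φ(1.960 − 2.817) = 0.196. Rounding does not rescue the entry.

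**Labelling.** It can fairly be said that 0.194 is a nominal spending total, so this is a matter of labelling. That is probably right. The row is nonetheless headed as accumulated beta and sits in the column with the 1.96 bound, where a reader will take it as attained error.

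**Practical weight.** The table is a projection. Real looks follow the DSMB's semi-annual calendar, and bounds at other event counts must come from the spending function. Replacing a total of 0.194 by 0.204 would shift the futility hazard ratios only from 1.027 to 1.024, 0.956 to 0.954 and 0.893 to 0.890. No board decision would plausibly turn on that. This stands, and it limits the point to minor weight.

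**A stronger reading.** A reader might infer that the trial is underpowered, that 381 events is wrong, or that the futility bounds must be rebuilt. The documents do not support this. Section 13.2 gives power as a whole percentage, and both 80.2% without looks and 79.7% with them round to 80%. Rebuilding the bounds from 0.204 gives an attained beta of 0.2039, against 0.2033 for bounds built from 0.194, so it gains no power.

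**Conclusion.** The point holds as a minor correction to the table in section 13.4.2. At HR 0.75, 381 events and a final Z of 1.96, the printed looks give an accumulated beta of about 0.203 and power of about 79.7%. The table's 0.194 implies 80.6%, which is 0.9 percentage points too high. It lies below the 0.198 that applies with no look at all.

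This rests on the plan's stated inputs, the usual normal approximation for the log-rank statistic, proportional hazards and a final bound held at 1.96. That 0.194 is the nominal spending total is an inference from its match with the interim entries; the documents do not say so. The mismatch at the second look is a separate small inconsistency in the same table.

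Section 13.2 is correct to rounding. Type I error, sample size and the final test are unaffected.

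**What to change.** Keep 381 events and the final bound of 1.96. In the section 13.4.2 table, do one of the following:

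- restate the final accumulated beta as about 0.203 (power about 79.7%); or
- label 0.194 as the nominal spending total and print the attained value of about 0.203 beside it.

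Reprint the table from one computation, so that the second look's Z, hazard ratio and accumulated beta agree. As printed, 0.96 and 0.033 fit Z 0.358, while Z 0.385 gives 0.952 and 0.034. The statistician should confirm from the design output which value was intended.

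The cost is a text and table correction. Raising the target to 385 events to bring power from 79.7% to 80.0% is not needed. Any estimate of its cost in time would also rest on the 30-month accrual model, and section 13.2 itself says that accrual was slower than anticipated.

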13.3 Primary Endpoint Analysis

Endpoints for efficacy use only invasive disease. Patients who withdraw consent for clinical or survival follow-up or lost patients will be censored at the date of withdrawal/loss according to disease and survival status known at that time.

13.3.1 Primary endpoint

The primary endpoint of this trial is invasive disease-free survival (iDFS), defined as time from randomization to the first occurrence of any one of the following events for invasive disease: Distant recurrence, locoregional recurrence, ipsilateral or contralateral breast cancer, second primary (non-breast) invasive cancer or death from any cause. Censoring will occur on the date the patient was last known to be alive and free from all invasive breast cancer and second invasive primaries.

13.3.2 Secondary Endpoint

Secondary endpoints for disease outcome include overall survival (OS) and distant disease free survival (DDFS). OS is defined as the time from randomization to death from any cause; surviving patients will be censored at the date last known to be alive. DDFS is defined as the time from randomization to the first occurrence of any one of the following events for invasive disease: Distant recurrence, second primary (non-breast) invasive cancer or death from any cause; censoring will occur at the date the patient was last known to be alive and free from distant invasive breast cancer and second invasive primaries.

Additional secondary endpoints include development of cardiovascular disease (including cerebrovascular events, myocardial infarction, or coronary artery disease requiring stent placement, angioplasty, or bypass surgery).

13.3.3 Analysis plans for primary and secondary endpoints

The primary analyses of iDFS will be performed in an intention-to-treat manner, in which all patients including those who do not begin protocol therapy will be analyzed according to their assigned arm. The primary determination of efficacy will be a time-to-event analysis using the Kaplan-Meier method for estimation, and the stratified log-rank test of iDFS to compare the aspirin arm versus the placebo arm (with stratum defined by hormone receptor status, BMI and stage), using the nominal alpha defined by the group sequential design, as given in [Section 13.4.2](#). A secondary analysis to estimate efficacy will use a multivariate Cox proportional hazard model to evaluate differences between arms after adjusting for stratification factors and the additional covariates of known importance to breast cancer including age, tumor size, and number of involved nodes. Identical models will be used to evaluate differences between arms in DDFS and OS.

Planned subgroup analyses will evaluate the hazard ratio of aspirin to placebo in subgroups defined by the study stratifiers of hormone-receptor status and enrollment time (HR positive and enrolled \leq 18 months from time from diagnosis vs HR positive and enrolled $>$ 18 months from diagnosis vs HR negative) and body-mass index (less than 30 kg/m^2 vs at least 30 kg/m^2). In addition to the WHO thresholds for underweight ($<18.5 \text{ kg/m}^2$), normal weight ($18.5\text{-}24.9 \text{ kg/m}^2$), overweight ($25\text{-}29.9 \text{ kg/m}^2$) and obese ($\text{BMI} \geq 30 \text{ kg/m}^2$), we will explore a linear association in the multivariate Cox model, based on the findings of Ligibel et al. that the prognostic relationship to disease-free survival with adjuvant chemotherapy was linear across the entire range of BMI observed at baseline. Further, an exploratory analysis will evaluate whether baseline factors are predictive of difference in clinical benefit of aspirin over placebo using multiplicative interactions in the Cox model. All tests of secondary objectives will use a two-sided Type I alpha of 0.05, and point estimates will be reported with 95% confidence intervals taken from Cox models.

Analyses of toxicity will be conducted on patients who receive at least one dose of aspirin or placebo. Toxicity will be reported by type and maximum grade using CTCAE v4.03 and contrasts of aspirin to placebo will use Fisher exact tests.

All study monitoring, data management and statistical analysis will be performed under the Alliance Statistics and Data Center.

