2.2 Secondary Objectives

2.2.1 To compare the effect of aspirin versus placebo in early stage HER2 negative breast cancer patients upon:

- a) Distant disease-free survival
- b) Overall survival
- c) Cardiovascular disease (see [Section11.3](#))

2.2.2 To compare the toxicity of aspirin versus placebo in early stage HER2 negative breast cancer patients.

2.2.3 To assess adherence to aspirin and placebo among early stage HER2 negative breast cancer patients.

2.2.4 To bank tumor and germline deoxyribonucleic acid (DNA), plasma and urine collected at baseline and sequential plasma and urine collected 2 years later for future measurement of inflammatory markers.

2.2.5 To determine if there are subgroups of participants characterized by lifestyle factors associates with greater inflammation for whom there is greater benefit of aspirin versus placebo upon iDFS.

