3.2 Eligibility Criteria

Use the spaces provided to confirm a patient's eligibility by indicating Yes or No as appropriate. It is not required to complete or submit the following page(s).

When calculating days of tests and measurements, the day a test or measurement is done is considered Day 0. Therefore, if a test were done on a Monday, the Monday 1 week later would be considered Day 7.

- **3.2.1** Histologic documentation of women or men with HER2 negative **breast carcinoma and free of recurrence**. If neoadjuvant therapy was received, either initial clinical stage (determined by physical and or radiologic examination) or post-operative pathologic stage can be used for eligibility purposes, with the higher stage determining eligibility. Histologic documentation of node positivity is required for ER/PR positive tumors.
Bilateral or synchronous breast cancers are allowed, as long as both cancers are HER2 negative and at least one of the cancers meets eligibility.
- **3.2.2** If ER and PR negative, tumor must be node positive or >2 cm and node negative. Patients must be registered within 18 months of diagnosis. pN1mic is eligible.
If ER and/or PR positive, tumor must be node positive and within 10 years of diagnosis. pN1mic is eligible.
- **3.2.3** Prior adjuvant treatment with chemotherapy and/or endocrine therapy, as determined by the treating physician, is allowed. The last dose of chemotherapy or radiation therapy must be at least 30 days prior to study registration. Concurrent hormonal therapy is allowed.
- **3.2.4** Regular NSAID/aspirin use at any dose (including baby aspirin) (defined as ≥ 5 days per week) is allowed if aspirin and/or NSAIDs are stopped for 30 days prior to study

entry and throughout the study period. Participants will be encouraged to use acetaminophen for minor pain and fever.

- **3.2.5** Age \geq 18 and $<$ 70 years of age.
- **3.2.6** ECOG performance status 0-2.
- **3.2.7** Patients with a prior history of gastric/duodenal ulcers documented on endoscopy can be enrolled as long as the ulcers did not cause bleeding requiring a blood transfusion/major intervention.

For patients who are Helicobacter pylori positive, a course of Helicobacter pylori eradication treatment must have been completed.
- **3.2.8** No history of GI bleeding requiring a blood transfusion, endoscopic or operative intervention.
- **3.2.9** No history of any prior stroke (hemorrhagic or ischemic).

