9.1 Routine Adverse Event Reporting

Adverse event data collection and reporting, which are required as part of every clinical trial are done to ensure the safety of patients enrolled in the studies as well as those who will enroll in future studies using similar agents. Adverse events are reported in a routine manner at scheduled times according to the study calendar in Section 5.0. For this trial, the Adverse Events: Solicited form is used for routine AE reporting in Rave.

Solicited Adverse Events: The following adverse events are considered "expected" and their presence/absence should be solicited, and severity graded, at baseline and for each cycle of treatment.

• CTCAE v 4.03 Term	• CTCAE v4.0 Organ Class (SOC)
• Gastrointestinal bleeding	• Gastrointestinal disorders
• Intracranial hemorrhage	• Nervous system disorders
• Epistaxis	• Respiratory, thoracic and mediastinal disorders
• Hematuria	• Renal and urinary disorders
• Dyspepsia	• Gastrointestinal disorders
• Gastritis	• Gastrointestinal disorders
• Bruising	• Injury, poisoning and procedural complications

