***Combinations of CTCAE Grade & Attribution Required for Routine AE Data Submission on Case Report Forms (CRFs)**

Attribution	Grade 1	Grade 2	Grade 3	Grade 4	Grade 5
Unrelated			a	a	a
Unlikely			a	a	a
Possible		a	a, b	a, b	a, b
Probable		a	a, b	a, b	a, b
Definite		a	a, b	a, b	a, b

- a) Adverse Events: Other CRF - Applies to AEs occurring between registration and within 30 days of the patient's last treatment date, or as part of the Clinical Follow-Up Phase.
- b) Adverse Events: Late CRF - Applies to AEs occurring greater than 30 days after the patient's last treatment date.

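### The toxicity comparison uses maximum grade without reference to the baseline grades collected for the solicited events, which dilutes any-grade and low-grade contrasts

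*Combined protocol and SAP*

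**What the plan says.** Comparing toxicity between arms is a secondary objective (section 2.2.2): "To compare the toxicity of aspirin versus placebo in early stage HER2 negative breast cancer patients". Section 13.3.3 sets the analysis population, "Analyses of toxicity will be conducted on patients who receive at least one dose of aspirin or placebo", and the method, "Toxicity will be reported by type and maximum grade using CTCAE v4.03 and contrasts of aspirin to placebo will use Fisher exact tests". The same section fixes the level: "All tests of secondary objectives will use a two-sided Type I alpha of 0.05".

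Section 9.1 lists seven solicited events: gastrointestinal bleeding, intracranial hemorrhage, epistaxis, hematuria, dyspepsia, gastritis and bruising. For these, "their presence/absence should be solicited, and severity graded, at baseline and for each cycle of treatment". The study calendar in section 5.0 likewise schedules an adverse event assessment before registration and then every six months.

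Neither 13.3.3 nor any other section says whether the baseline record enters the maximum, whether only new or worsened grades count, or whether the contrast is adjusted for baseline grade.

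**The concern.** The trial collects what is needed to separate symptoms that patients bring with them from symptoms that arise on study drug, and then leaves that information out of the stated comparison.

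Dropping the pre-dose record from the maximum would not solve this. The events are solicited again at each cycle, so a patient with grade 1 dyspepsia before the first tablet and the same dyspepsia afterwards has grade 1 on treatment. Only a comparison of the on-treatment grade with the patient's own baseline grade removes that case.

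Baseline symptoms are plausible in this population. Section 3.2.7 allows an ulcer history: "Patients with a prior history of gastric/duodenal ulcers documented on endoscopy can be enrolled as long as the ulcers did not cause bleeding" (the sentence goes on to specify bleeding that needed transfusion or major intervention). Section 3.2.3 allows earlier chemotherapy and concurrent hormonal therapy.

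At stake is sensitivity to the frequent, low-grade gastrointestinal and bruising effects of a drug taken daily for five years. In a harm comparison, dilution towards no difference is the less safe direction.

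**Working it through.** **The plan's own figures.** The documents give no power calculation, event rate or baseline prevalence for toxicity, so there is no toxicity figure to reproduce. The only design calculation for the randomised comparison is 381 iDFS events (section 13.2). It reproduces: 4 × (1.960 + 0.842)² / (ln 0.75)² = 31.40 / 0.0828, or about 380 events. The point here does not depend on it.

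**Inputs from the documents.** Total 2936 with equal allocation (sections 13.2 and 7.0) gives 2936 / 2 = 1468 per arm, taking all patients as dosed. The test is two-sided at 0.05 (section 13.3.3).

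**Assumed inputs.** New any-grade events occur in 10% (placebo) and 13% (aspirin) of patients free of the symptom at baseline. Baseline prevalence b is 0, 5, 10 or 20%. Baseline symptoms persist unchanged on treatment.

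**Formulas.** With new-event rate i in an arm:

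- all events counted: rate = b + (1 − b) × i
- emergent events only: rate = (1 − b) × i
- the risk difference is (1 − b) × (0.13 − 0.10) under both definitions
- power = Φ[(d − 1.96 × se0) / se1], where d is the risk difference and se0 and se1 are the pooled and unpooled standard errors

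**Worked case, b = 10%.**

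- All events: 0.10 + 0.90 × 0.10 = 19.0% versus 0.10 + 0.90 × 0.13 = 21.7%. RR = 1.14, d = 0.027, se0 = 0.01486, se1 = 0.01485. Power = Φ(−0.14) = 44%.
- Emergent only: 9.0% versus 11.7%. RR = 1.30, d = 0.027, se0 = 0.01124, se1 = 0.01123. Power = Φ(0.44) = 67%.

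**Range.**

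| Baseline prevalence | Risk difference (both) | All events: RR, power | Emergent: RR, power |
|---|---|---|---|
| 0% | 3.00 points | 1.30, 72% | 1.30, 72% |
| 5% | 2.85 points | 1.20, 56% | 1.30, 70% |
| 10% | 2.70 points | 1.14, 44% | 1.30, 67% |
| 20% | 2.40 points | 1.09, 30% | 1.30, 61% |

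**Other assumed effects** (power, all events versus emergent):

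- 10% versus 14%: 79% versus 90% at 5% prevalence; 67% versus 88% at 10%; 48% versus 84% at 20%.
- 5% versus 8%, 20% prevalence: 32% versus 83%.
- 10% versus 15%: 97% versus 98% at 2% prevalence; 93% versus 98% at 5%.

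**Type I error.** Simulated Fisher tests with equal arms (10% new events in each) rejected in 4.8% of trials at 0% baseline prevalence and 3.8% at 20%, so there is no inflation.

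The power figures are normal approximations. Fisher's exact test is slightly more conservative.

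**The case against.** **The plan is silent, not wrong.** Section 13.3.3 nowhere says that an unchanged baseline symptom is a toxicity case, and the separate baseline grade leaves a baseline-aware derivation open. That is true of the wording. But maximum grade, read plainly, has no baseline term, and repeat solicitation carries unchanged symptoms into the on-treatment maximum. A programmer who followed the text would count them.

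**Randomisation protects the comparison.** This stands. Pre-existing symptoms balance in expectation, neither arm is favoured and type I error is not inflated. The absolute risk difference is identical under both definitions, so a reader who infers that the analysis hides aspirin's effect goes too far. What is lost is precision, and the relative risk moves towards 1.

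**Maximum grade still shows worsening.** This also stands. A move from grade 1 to grade 2 or 3 is visible in a table by maximum grade, and the any-grade model above gives baseline-symptomatic patients no way to worsen. The loss therefore belongs to any-grade and low-grade contrasts. Grade 3 or higher events should be little exposed because few patients should have them at entry: section 3.2.8 excludes a history of gastrointestinal bleeding that needed transfusion or intervention, and section 3.2.9 excludes prior stroke.

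**Baseline prevalence may be low.** Eligibility also requires regular aspirin or NSAID use to have stopped for 30 days, chemotherapy to have ended at least 30 days earlier, and *Helicobacter pylori* to have been treated where positive. An ulcer history is not current dyspepsia. This is fair: at 2% to 5% prevalence with a larger effect, the loss is only 1 to 5 percentage points of power.

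**A tempting extra argument fails.** A reader might infer that pre-dose symptoms also enter through the Adverse Events: Other form, whose window in section 9.2 opens at registration: "Applies to AEs occurring between registration and within 30 days of the patient's last treatment date". That form is separate from the solicited one. It takes no grade 1 events, and grade 2 only when attribution is at least possible. It does not support the point about solicited dyspepsia, gastritis or bruising.

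**Conclusion.** The point holds as a loss of sensitivity in a secondary safety comparison. As written, the analysis makes no use of the baseline grades, so unchanged pre-existing symptoms count in both arms. The relative risk is attenuated and power is lost for any-grade and low-grade contrasts of the solicited events. With 10% versus 13% new events, the loss is 14 percentage points of power at 5% baseline prevalence (70 − 56), 23 at 10% (67 − 44) and 31 at 20% (61 − 30).

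These sizes rest wholly on assumed event rates, assumed prevalence and persistence of the baseline symptom; only the direction follows from the documents. The documents do not support a claim of bias against one arm, of a distorted absolute excess, or of a material effect on serious bleeding. The primary endpoint and futility monitoring are untouched. Because a more sensitive method is available from data already collected, the change should be made.

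**What to change.** In section 13.3.3, add that for the solicited events the arm contrasts use the maximum grade after the first dose that is new or worse than the patient's baseline grade for the same term. Tabulate baseline grades by arm, and keep the unadjusted maximum grade as a supporting table. State how a missing baseline grade is handled.

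The cost is a sentence or two in the statistical section, one derived variable and one extra table. No new data are needed, and the sample size does not change. Writing the rule down before unblinding also removes a later choice between definitions.
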